5.7 IND

Dr. [REDACTED] holds the IND #162060 and is acting as the Sponsor-Investigator for this study.

5.8 Provision of Investigational Product to Participants

Following receipt of confirmed subject eligibility and consent, IDS will randomize subjects as described below in Section 6.1. IDS will prepare the courier or overnight mail service, which will deliver IP to participants according to the below dosing schedule.

Clear instructions will be provided to the subject regarding the number and type of capsules to be ingested at each IP administration time point listed.

DOSING SCHEDULE

Antihistamine and Placebo Arm Dosing^{1,2}

Day 0-Day 84:

Cetirizine 10 mg or placebo (1 capsule) QD
Famotidine 20mg or placebo (1 capsule) BID

1. Dose to be assessed at Day 14. Subjects unable to tolerate will be withdrawn from study
2. Subjects receive initial shipment of 28 days' supply at Day 0, and shipment of remaining 56 days' supply after Day 14 assessment

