7.2 Population for Analysis

The following populations will be used in the analyses:

- Intent-to-treat (ITT): All subjects who received at least one intake of IP. Subjects will be analyzed according to their assigned treatment.

- Per protocol (PP): All subjects in the ITT population who were free from major protocol violations that could lead to bias
- Safety: All subjects who received at least one intake of IP. Subjects will be analyzed according to the treatment they actually received.

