24 subjects are needed to complete the research procedures. We anticipate enrolling and screening approximately 36 subjects to reach this goal, given screen failure and possible study drop-out/withdrawal. Screen failures will be replaced; drop-out/withdrawal/lost to follow-up will not be replaced. Participants will be drawn from the state of GA. We project enrollment to reflect the incidence of PASC between the sexes of 70% female and 30% male. PASC incidence among races is unknown.

15. Recruitment Methods

Recruitment will be done through a two-pronged approach utilizing direct engagement with Long COVID clinics at Grady and Emory.

We will engage with clinicians at PASC and primary care clinics at Emory and Grady. Promotion will entail a combination of direct outreach and education from our team along with materials such as flyers and pamphlets.

The study team will review medical records for Emory and Grady PASC Clinic patients to identify potentially eligible prospective subjects, per protocol Section 11 Inclusion and Exclusion Criteria.

Finally, we will share our graphics with Emory's communications team and request placement on their website and dissemination of information about the trial.

16. Withdrawal of Participants

Participants may discontinue IP or withdraw from the study at any time and for any reason without prejudice to their medical care. Furthermore, the PI may discontinue a subject from IP or withdraw them from study procedures. The reason for the patient's discontinuation or withdrawal will be recorded in REDCap.

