16.1 Discontinuation of IP

Discontinuation refers to the subject stopping IP administration. Subjects who discontinue IP should, with their consent, continue participating in the study, completing all visits and assessments as scheduled. The reason for IP discontinuation will be recorded in REDCap.

Possible reasons for IP discontinuation are:

- If the subject requests discontinuation of treatment with IP
- If the subject requires treatment with a prohibited concomitant medication
- If the subject develops contraindications to any of the IPs
- If clinical reasons arise where the harm is considered to outweigh the benefits by the Investigator
- If the subject no longer meets inclusion/exclusion criteria
- Occurrence of intolerable adverse reactions and pregnancy
- Unblinding (accidental or medically necessary) of subject, investigator, or study staff

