16.2 Withdrawal from Study Procedures

Withdrawal refers to a study participant's stopping IP and all study assessments and visits.

If a subject withdraws his/her consent for future collection of information, the Investigator may retain and continue to use any data collected before consent was withdrawn.

Every effort should be made to ensure that subjects who withdraw or are withdrawn undergo an early withdrawal study visit as soon as possible.

Possible reasons for withdrawal include:

- The subject requests to withdraw

- The subject withdraws consent to the collection, use and sharing of his/her data
- The Investigator thinks that study participation is no longer in the best interest of the subject
- The Investigator thinks that the subject is at significant risk of failing to comply with the provisions of the protocol so as to cause harm to her/himself or seriously interfere with the validity of the study results
- At the request of the ethics committee or regulatory authorities in the exercise of their duties
- Loss to follow-up
- The study is terminated

All data from subjects withdrawn from the study may be analyzed up until time of withdrawal.

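### Section 5.8 withdraws subjects who cannot tolerate the dose at Day 14 from the study, while Section 16.1 stops only their IP and keeps them in follow-up

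*Combined protocol and SAP*

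**What the plan says.** The Section 5.8 dosing schedule has the dose assessed at Day 14, and its note 1 adds: "Subjects unable to tolerate will be withdrawn from study".

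Section 16 separates two events. Withdrawal (16.2) means "stopping IP and all study assessments and visits". IP discontinuation (16.1) means stopping the product only, and its follow-up rule is: "Subjects who discontinue IP should, with their consent, continue participating in the study, completing all visits and assessments as scheduled". The possible reasons listed in 16.1 include "Occurrence of intolerable adverse reactions and pregnancy". The reasons listed in 16.2 do not name intolerance.

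The opening of Section 16 gives a general power: "Furthermore, the PI may discontinue a subject from IP or withdraw them from study procedures". For those who leave, 16.2 adds: "Every effort should be made to ensure that subjects who withdraw or are withdrawn undergo an early withdrawal study visit as soon as possible".

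Section 7.2 defines the ITT population as "All subjects who received at least one intake of IP. Subjects will be analyzed according to their assigned treatment". Section 4 makes the percentage of subjects completing 70% of PRO surveys at 12 weeks a secondary endpoint, and Section 7.4.1 tabulates it under attrition.

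**The concern.** The same subject, with the same problem at the same visit, gets two instructions, both in terms the protocol has defined. Staff at the Day 14 contact cannot tell which to follow, and two coordinators could treat identical subjects differently.

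The choice matters because retention and questionnaire completion are themselves endpoints here. Every full post-baseline PRO battery falls after Day 14, so following 5.8 leaves the subject with none on the schedule. The survey-completion percentage would then partly reflect a protocol rule rather than whether people are willing and able to complete the forms remotely. A subject removed by rule is also, on a plain reading, neither lost to follow-up nor a voluntary termination, so neither of those two attrition percentages captures the exit. Finally, the exploratory changes from baseline at Weeks 6, 9 and 12 cannot be calculated for that subject, and the reason they are missing is related to treatment.

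**Working it through.** **Setting the rules side by side**

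| | Section 5.8, note 1 | Section 16.1 |
|---|---|---|
| Trigger | Dose not tolerated at Day 14 | Intolerable adverse reaction, any time |
| Action | Withdrawal from study | IP stopped |
| Visits and forms afterwards | None scheduled (definition in 16.2); early withdrawal visit attempted | All, with consent |
| Force | Automatic | Expected |

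Reading 5.8 loosely as withdrawal from IP would reconcile the two, but the note says study, and Section 7.5 (Subject Disposition) counts IP discontinuations and study withdrawals on separate lines.

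**Inputs for the per-subject effect** (the plan gives no figure of its own to reproduce)

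- Baseline PROs: 7 (Section 6.5.1).
- Post-baseline PROs: 7 instruments × 3 visits (Days 42, 63, 84; Section 6.5.6) = 21. By Day 14: 0.
- Weekly forms: 4 × 12 weeks = 48 (Section 6.5.5). By Week 2: 4 × 2 = 8.
- End of Study survey: 1, also due at early termination (Section 6.5.7), so counted as done.
- Symptom survey: two additional screening marks in the Section 6.7 table.

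**Assumption.** The denominator is every form scheduled through Week 12, which is how we read the endpoint's reference to 12 weeks. The plan does not say which forms count, so several rules were tried.

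Completion = forms done by Day 14 (plus the End of Study survey where counted) ÷ forms scheduled through Week 12:

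| Forms counted | Completion if withdrawn at Day 14 |
|---|---|
| Post-baseline PROs | 0/21 = 0% |
| + End of Study survey | 1/22 = 4.5% |
| Post-baseline PROs + weekly forms | 8/69 = 11.6% |
| All forms | (7 + 8 + 1)/(7 + 21 + 48 + 1) = 16/77 = 20.8% |
| Baseline + post-baseline PROs | 7/28 = 25.0% |
| Same + End of Study survey | 8/29 = 27.6% |
| Same + symptom survey (12 weekly, 2 screening) | (8 + 2 + 2)/(29 + 14) = 12/43 = 27.9% |

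Counting the headache diary as 7 daily entries instead of one form gives 0/39 = 0%, 13/52 = 25.0% and 14/53 = 26.4% for the corresponding rows, inside the same range.

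If one full 7-instrument battery is obtained at the early withdrawal visit (its content is not specified, so this is also an assumption), the numerator rises by 7:

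- lowest: (8 + 7)/69 = 15/69 = 21.7%
- post-baseline PROs only: 7/21 = 33.3%
- baseline + post-baseline PROs: 14/28 = 50.0%
- highest: (8 + 7)/29 = 15/29 = 51.7%

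In all, 72 counting rules were enumerated. Leaving baseline out gives 5 (0 to 4 weekly forms). Counting baseline gives 1 + 4 × 3 = 13 (0 to 2 screening symptom surveys whenever a weekly form counts). Then 18 × 2 (End of Study survey in or out) × 2 (diary as 1 or 7 entries) = 72. None reaches 70%, with or without the extra battery. Under 16.1 every form remains available, so the ceiling is 100%.

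**Weekly AE logs.** Weeks 3 to 12 are lost: 10 of 12.

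**The case against.** The strongest reply is that the texts can coexist. Section 5.8 is a specific rule for one scheduled check and 16.1 a general one. Both reason lists in Section 16 are headed as possible reasons, 16.1 says only that subjects should continue, and the PI may choose either route. A site could apply 5.8 at Day 14 and 16.1 otherwise without breaking a mandatory sentence. This softens the conflict but does not remove it: the PI's powers are case-by-case judgements, note 1 is automatic, 16.1 covers everyone who stops IP and names intolerance, and no text marks 5.8 as an exception.

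The second reply is that failing the 70% threshold depends on the denominator and population. If only forms due while enrolled counted, a Day 14 withdrawal could score 16/16 = 100%, and the 72 rules do not vary that choice. The dependence is real and is stated as an assumption. But that reading would score someone who left at Week 2 as a completer on a measure filed under attrition, so it is the less natural one. Section 7.4.1 names no population. The ITT and safety definitions both retain anyone with one intake of IP, and a withdrawal made as the protocol directs is not obviously a violation that would remove the subject from the per-protocol set.

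Third, counting an early leaver as a non-completer is what an attrition measure should do. That is fair when the subject chooses to leave. It is less informative when the plan removes someone who would have stayed.

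Fourth, much is unaffected. The dose-adherence endpoint and the count of IP discontinuations come out the same under either rule. The End of Study survey is kept, SAEs are followed, data up to withdrawal are used, and reasons are listed by arm. The AE logs lost fall after IP stops, so little on-treatment safety information goes. Section 14 sizes enrolment "given screen failure and possible study drop-out/withdrawal", and both drugs are described as well tolerated. All of this stands and is why the point is minor.

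**Conclusion.** The inconsistency is real. Sections 5.8 and 16.1 give different instructions for a subject who cannot tolerate the dose at Day 14, and the plan does not say which prevails. Per affected subject, following 5.8 removes three of three post-baseline PRO batteries and 10 of 12 weekly AE logs from the schedule. It also holds survey completion to 0% to 28% (22% to 52% with a full early-withdrawal battery), against up to 100% under 16.1. The completion figures rest on all forms scheduled through Week 12 being the denominator; failing the endpoint also assumes that the analysed population keeps these subjects.

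No effect on the trial-level percentage is claimed. The plan states neither an intolerance rate nor the number to be treated: in Section 14, 24 is the number needed to complete and about 36 the number to be enrolled and screened. The number affected could be zero. Severity is minor, with high confidence that the texts conflict.

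**What to change.** Replace the second sentence of note 1 in Section 5.8 with wording such as: *Subjects who cannot tolerate the dose stop IP and, if they consent, remain in follow-up with every planned visit and assessment, as set out in Section 16.1.*

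The cost is one sentence, plus continued remote questionnaires and weekly logs for each subject who agrees to stay. Stipends under Section 19 add at most 3 × $50 = $150 per such subject.

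If full withdrawal is what the sponsor wants, an explicit exception in 16.1 for Day 14 intolerance would also remove the contradiction, but it would keep the loss of follow-up data. The first option is preferable because it retains those data.

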5.9 Acquisition

A sufficient quantity of the FDA-approved or compounded formulation of famotidine, cetirizine and placebo for the study will be purchased and distributed by the Emory Investigational Drug Services (IDS). Emory IDS was chosen because of its experience in the compounding of medications for clinical trials, available formulations and strengths, assays for potency, and ability to provide matched placebos.

5.10 Accountability and Destruction Procedures

Subjects will not be required to return any excess drug capsules to the facility. Subjects will dispose of excess drug capsules locally, ensuring that the child-protection closure system is intact.

5.11 Treatment Adherence

Treatment adherence will be measured by subjects completing a weekly assessment of their IP adherence by completing a study adherence log. The CRC will also review remaining pill count with the subject during study visits to inform adherence.

6. Procedures Involved

[figure not shown]
6.1 Study Design

This is a fully decentralized, single center, randomized, double-blind, placebo controlled, clinical trial to evaluate the safety, tolerability, and feasibility of a potential treatment for PASC.

Upon confirmation of eligibility, the investigational pharmacist will randomize subjects 2:1 treatment versus placebo. Treatment consists of 10mg of cetirizine daily and 20mg of famotidine twice daily. Placebos will match the morphology of the treatments but contain no active ingredients. Study subject and study team will be blind to assigned treatment; only the IDS will be unblind.

Subjects will be followed for safety, tolerability, and responses to patient reported outcome (PROs) over 12 weeks. At Week 12, End of Study, subjects will be required to complete a questionnaire that addresses several aspects of feasibility of participating in the study.

6.2 Study Schema

6.3 PRO Collection—Feasibility and Efficacy Assessments

Subjects will complete the following PROs at protocol specified timepoints as described in Section 6.5 and as detailed in the Schedule of Events in Section 6.7. Subjects with difficulty completing the PROs in Emory's Part 11 compliant REDCap instance will be contacted by CRC via telemedicine or telephone. In these encounters, CRC will administer PRO surveys and collect symptom tracking data at protocol designated study time points.

- **PROMIS Fatigue 7A**—measures fatigue with daily activities
- **Insomnia Severity Scale**—measures difficulty sleeping
- **PROMIS Cognitive 6A**—measures difficulty thinking and concentrating
- **DePaul Symptom Questionnaire (DSQ-1) Short form**—measures post-exertional malaise
- **COMPASS 31**—measures symptoms of dysautonomia

- **WHO Disability Assessment Schedule (WHODAS 2.0)**—measures health and disability
- **Headache Diary**—measures the number and severity of headaches (completed daily during the 7 days prior to study visit)
- **Self-reported Persistent Symptoms Survey**—measures presence or absence of Long COVID symptoms and their severity
- **Concomitant Medications Log**—records subject-reported medications, supplements and vitamins
- **Self-reported Changes to Health Log**—records subject-reported adverse events
- **IP Adherence Log**—records subject-reported adherence to IP dosing regimen
- **End of Study Survey**—assesses the feasibility and acceptability of methods and procedures

6.4 Safety Assessments

Subjects will report signs and symptoms of changes to their health weekly. In addition to examining the subject's electronic medical record (EMR), the CRC will assess for AEs and SAEs by reviewing the subject's AE log and talking to the patient. AEs and SAEs will be reported as defined by 21 CFR 312. All SAEs must be followed until resolution/stabilization or until a time that is determined by the Investigator.

6.5 Detailed Study Procedures and Assessments by Study Period/Study Day

The procedures performed during this study will be performed according to this section and the Schedule of Events table shown in Section 6.7 below.

6.5.1 Screening (Within 28 days ± 3 days of Day 0):

Prior to any study-specific procedures or data collection, the CRC will obtain informed consent from potentially eligible subjects. If the subject is not an Emory patient, the subject will be asked to sign a medical release form. Using a verbal consent, subjects will be prescreened by televisit by the CRC who will review the inclusion/exclusion criteria. Subjects who remain interested and are potentially eligible will then be consented, and medical records will be sought from the subject's healthcare system to confirm eligibility.

The following procedures and data collection will be performed during Screening:

- Signature of electronic Informed Consent Form and provision of subject information

- Collection of sociodemographic data
- Medical record review
- Collection of medical and surgical history, including acute COVID-19 history, PASC history (time from symptom onset or positive SARS-CoV-2 testing), and COVID-19 vaccination status
- Assessment routine concomitant medications
- Assessment of baseline PROs:
 - WHODAS 2.0 36-item score
 - PROMIS Fatigue 7a
 - Insomnia Severity Index
 - PROMIS Cognitive Function Short Form 6A
 - DSQ-PEM Short Form
 - Headache Diary (completed daily during the 7 days prior to visit)
 - COMPASS 31
- Confirm Inclusion and Exclusion criteria

6.5.2 Randomization/Day 0 will be a televisit with the study physician for a baseline evaluation to confirm eligibility. Study clinician will confirm adequate hepatic and renal function after onset of Long COVID symptoms through review of participant's labwork in historical medical records. Study clinician will confirm negative pregnancy status in participants capable of becoming pregnant via urine or serum β -HCG within 30 days of randomization/Day 0. Women of childbearing potential who don't anticipate a pregnancy test at a clinician's office within 30 days of randomization will be mailed a urine pregnancy test kit by study staff. Subjects will take the pregnancy test during the Randomization/Day 0 televisit and show the result to the study physician. If additional physical exam is needed per study physician discretion, the study physician will conduct a telemedicine exam of the following systems: Constitution, Head, eyes, ears, nose and throat, Cardiovascular, Respiratory, Gastrointestinal, Genitourinary (CVA tenderness per subject exam), Musculoskeletal, Skin, Neurological, Psychological. Subjects will be asked to report their most burdensome PASC symptom at Day 0.

Upon confirmation of eligibility, subjects will be randomized as described in Section 6.1 and shown in Section 6.2.

6.5.3 Day 1: Participant receives IP and self-administers.

6.5.4 Days 2-84: Participant takes IP daily

6.5.5 Weekly: Participant completes adverse event log, study medication adherence log, concomitant medication log, self-reported persistent symptoms questionnaire

6.5.6 Days 42, 63, and 84, all +/- 3 days, subjects enter patient reported outcome (PRO) data into REDCap.

- PRO data to be collected
 - WHODAS 2.0 36-item score
 - PROMIS Fatigue 7a
 - Insomnia Severity Index
 - PROMIS Cognitive Function Short Form 6A
 - DSQ-PEM Short Form
 - Headache Diary (completed daily during the 7 days prior to visit)
 - COMPASS 31

6.5.7 Day 84/End of Study (EOS) or Early Termination: Participants complete End of Study survey

6.6 Subject Contact Schedule

Subject contact will occur at designated time points per protocol via televisit or phone call. To ensure data quality, study personnel may contact subjects at unscheduled timepoints to obtain clarifying information on adverse events, provide supplemental training on REDCap data entry, or to remind overdue participants to complete the scheduled patient-reported outcome surveys according to the study schedule. Study subjects may also initiate unscheduled contact with study staff for help with any questions, concerns, or difficulties.

Protocol Title: Treatment of Long COVID (TLC) Feasibility Trial: Feasibility Assessment of a Decentralized Platform Double-blind, Randomized, Controlled Trial Investigating Repurposed Drugs in the Treatment of Post-Acute Sequelae of Coronavirus-19 (PASC)

6.7 Schedule of Events

Weeks	Screening				Rand		Dose 1		Treatment Phase												EOS	
	Week -4	Week -3	Week -2	Week -1	Week 0		Week 1	Week 2	Week 3	Week 4	Week 5	Week 6	Week 7	Week 8	Week 9	Week 10	Week 11	Week 12				
Days	Day -28	Day -21	Day -14	Day -7	Day 0	Day 1	Day 7	Day 14	Day 21	Day 28	Day 35	Day 42	Day 49	Day 56	Day 63	Day 70	Day 77	Day 84				
Visit Window^a																						
Informed Consent	X				± 3 days	+3 days	± 3 days	± 3 days	± 3 days	± 3 days	± 3 days	± 3 days	± 3 days	± 3 days	± 3 days	± 3 days	± 3 days	± 3 days				
Inclusion/Exclusion	X				X																	
Subject app training	X																					
Demographics	X																					
Concomitant Medications		X			X	X	X	X	X	X	X	X	X	X	X	X	X	X	X	X	X	
Telehealth Physical Exam ^b		X			X																	
Medical/Surgical History ^c		X			X	X																
Dispense (mail) UPT ^d	X																					
UPT ^e					X																	
Query for subject-assessed worst symptom						X									X			X		X		
Randomization						X																
Dispense IP						X																
IP Dosing																				Day 1 daily through End of Study (Day 84)		
Tolerability assessment																						
IP Adherence Log							X	X	X	X	X	X	X	X	X	X	X	X	X	X	X	
WHODAS			X																			
DSQ-PEM			X																			
PROMIS Fatigue 7a			X																			
Insomnia Severity Scale			X																			
Headache Diary ^f			X																			
PROMIS Cognitive Function 6a			X																			
COMPASS 31			X																			
Symptom Survey			X	X			X	X	X	X	X	X	X	X	X	X	X	X	X	X	X	
Adverse Event Collection ^g					X	X	X	X	X	X	X	X	X	X	X	X	X	X	X	X	X	
Televisit or telephone contact ^h	X				X	X																
Issue Stipend					X																	
End of Study Survey																						

a. Visit weeks and windows are calculated from Day 1
b. Telehealth PE to be completed at any time during Screening Phase or on Day 0 pre-randomization, if not available in medical records
c. Med/Surg Hx collected up to time of first dose; AE collected after completion of first dose
d. For WOCBP
e. UPT conducted during Day 0 televisit with visual confirmation of results
f. Subjects receive initial shipment of 28 days' supply at Day 0, and shipment of remaining 56 days' supply after Day 14 assessment
g. Headache diary to be completed in REDCap daily Days -7 to Day -1 and daily for the 7 days preceding SVs at Weeks 6, 9 and EOS
h. Televisit/telephone call required at Days -28, 0, 1, 14 and as needed for dose tolerability assessment and query resolution at subsequent SV days. Unscheduled visits at request of study team or subject are permitted.

7. Statistical Analysis Plan

